**Table 9 Expected Mean Ratios and Coefficients of Variation for CHTP 1.2/CC after 90 Days of exposure**

	CHTP 1.2/CC MR (CV)
Total NNAL	0.30 (0.60)

Abbreviations: Total NNAL = Total 4-(methylnitrosamino)-1-(3-pyridyl)-1-butanol; MR = Mean ratio; CHTP 1.2 = Carbon Heated Tobacco Product 1.2; CC = Combustible cigarettes; CV = Coefficient of variation.

The power to detect a reduction was computed and is presented below.

Table 10 describes the expected power to detect a reduction of 50% or more in the levels of MHBMA, 3-HPMA, S-PMA, and COHb in CHTP 1.2 arm compared to the CC arm after 5 days of exposure and total NNAL after 90 days of exposure, with a one sided test with 2.5% type I error probability using the assumptions from YVD-CS01-EU and, and 120 randomized subjects in a 2:1 ratio (80 in CHTP 1.2 arm and 40 in CC arm). It is assumed that a minimal number of subjects will be excluded from the PP set in confinement for both arms and CC in ambulatory, whereas at least 50% will remain in the PP set in ambulatory for CHTP 1.2, therefore a 2:1 randomization ratio was chosen.

Table 10 Expected Power

Assumptions	Reduction					
	50%	51%	52%	53%	54%	55%
YVD-CS01-EU	94%	88%	81%	70%	56%	38%

The test-wise powers to detect a reduction of 50% or more in the levels of MHBMA, 3-HPMA, S-PMA, and COHb on Day 5 and in total NNAL after 90 days in smokers switching from CC to the CHTP 1.2 as compared to smokers continuing to use CC, using a one-sided test with 2.5% type I error probability using the assumptions from YVD-CS01-EU, and 120 randomized subjects in a 2:1 ratio (80 in CHTP 1.2 arm and 40 in CC arm) are described in **Table 11**.

Table 11 Test-Wise Power

Parameter	Test-Wise Power
COHb	96%
3-HPMA	>99%
MHBMA	>99%
S-PMA	>99%

Total NNAL 98%

Given the above calculation, the sample size was considered sufficient to have more than 80% power to detect a reduction of 50% or more in the levels of MHBMA, 3-HPMA, S-PMA, and COHb in CHTP 1.2 arm compared to the CC arm after 5 days of exposure, and in the levels of total NNAL in the CHTP 1.2 arm compared to the CC arm after 90 days of exposure, using a one sided test with 2.5% type I error probability.

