10 ANALYSIS POPULATIONS

The study population characteristics will be described on the Safety Population, FAS, (if different from Safety Population), and on the Per-Protocol populations for Period 1 and 4. The per-protocol populations will be the primary analysis set for biomarkers of exposure, cotinine and nicotine in plasma, CYP1A2, CYP2A6, Ames Mutagenicity test, clinical risk endpoints, FTND, mCEQ, ITUQ, Cough and QSU-brief. The Full Analysis Set will be the primary analysis set for exposure to product, compliance to randomization arm, Prochaska and SES. Exposure and questionnaires, as a secondary analysis, will be described by randomization arm and product use category using the full analysis set. If the FAS and PP population differ, the biomarkers of exposure tables will be repeated on the FAS.

Safety will be analyzed using the safety population.

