12.5.2.4 Spirometry

Spirometry parameters assessed during the study include:

- Measured forced expiratory volume in 1 second (FEV₁)
- Measured forced vital capacity (FVC)
- FEV₁/FVC
- Percent of predicted FEV₁ (% pred)
- Percent of predicted FVC (% pred)
- Measured FEF 25 - 75
- Measurement interpretation (categories: normal, abnormal, abnormal clinically significant)

The above data are collected at Screening, Day 6, and Day 90 Visit. At Screening, data are collected at least one hour after having stopped smoking. On Day 6 and Day 90 Visit, spirometry has to be done prior to smoking.

It is assumed that these parameters are normally distributed.

Spirometry data values and normal/abnormal will be listed by arm and study day (Listing 15.3.4.3). Assessments performed after baseline will be listed together with change from

baseline and shift in normality. Spirometry data from subjects who had significant clinical findings will be highlighted in listings.

Descriptive statistics will be presented for FEV₁(L), FEV₁ (% pred), FVC(L), FVC(% pred), FEV₁/FVC, FEF (measured) at baseline, on Day 6 and at Day 90 Visit by arm, and overall for the safety population and for the PP population. Spirometry data will be summarized together with changes from baseline for data with and without bronchodilator (Table 15.2.4.19.x). The number and percentage of subjects with normal/abnormal/abnormal clinically significant results will be presented in Table 15.2.4.20.X.

For the PP population, the analysis will compare the Day 6 and Day 90 Visit values between the CHTP 1.2 and CC arms. An ANCOVA model will be used with terms for sex, average daily CC consumption over the last 6 weeks as reported during admission and arm. The SAS code will be the same as described in Section 12.5.1.1 “Primary endpoints”; but then without a log-transformation.

The least squares (LS) means and estimate of the difference along with its 95% CI will be presented in the tables. The LS means for each arm along with the difference and 95% CI will be presented in the table (Table 15.2.4.21).

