  random _residual_/subject=usubjid type = un;  
  lsmeans trtan*avisit ;  
run;
```

For the confinement period, a similar model will be run, replacing the product use category with the treatment arm (Table 15.2.4.25.X).

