The profiles of the means (geometric for parameters analyzed in logarithmic scale and arithmetic for parameters analysed in natural scale) per time point will be produced for all endpoints except HbA1c, Apo A1, Apo B, weight and waist circumference which are only assessed at baseline and Day 90 Visit (Figure 15.1.2.29–46).

For all endpoints, an ANCOVA model will be used on Day 5 and on the Day 90 Visit (as applicable). The SAS code will be the same as described in Section 12.5.1.1 “**Primary endpoints**”; except that there will only be a log transformation of the endpoints as specified above. For HbA1c, Apo A1, Apo B, waist circumference and body weight; the analysis will compare the Day 90 Visit values.

As applicable, geometric LS means for each arm along with the % reduction (100% - CHTP 1.2 : CC Ratio (%)) for hs-CRP, blood glucose, TG, TC, fibrinogen, homocysteine, sICAM-1, platelets and 11-DTX-B2 or the arithmetic LS means along with the difference (CHTP 1.2 - CC) for the other endpoints; per timepoint with 95% CI will be presented in the table. (Table 15.2.4.28).

All figures, summaries and analyses will be performed on the Per Protocol Populations.

If applicable, the tables with descriptive statistics will be repeated for the group of subjects who attempt to quit (see section “**10.7 Quitters Population**”).

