12.5.2.7 Risk Endpoints related to Oxidative Stress

The following risk endpoints related to oxidative stress will be assessed:

- Epi-prostaglandin F2 α (8-epi-PGF2 α) in 24-hour urine at baseline, Day 5, Day 30 Visit, Day 60 Visit, and Day 90 Visit (expressed as concentration adjusted for creatinine)
- Ratio of 8-epi-prostaglandin F2 α (8-epi-PGF2 α) to prostaglandin F2 α (PGF2 α) in plasma at baseline, Day 5 and Day 90 Visit (results only listed).
- 8-Hydroxy-2'-deoxyguanosine (8-OHdG) in 24-hour urine at baseline, Day 5, Day 30 Visit, Day 60 Visit, and Day 90 Visit (expressed as concentration adjusted for creatinine)
- Total anti-oxidant capacity (TAC) in serum at baseline, Day 5 and Day 90 Visit.

It is assumed that all oxidative stress parameters are log-normally distributed.

These clinical risk endpoints will be summarized and listed by arm, subject, parameter and time point, together with changes from baseline (Listing 15.3.4.6).

The actual values, along with the percent change from baseline will be summarized (Table 15.2.4.29).

The profiles of geometric means per time point will be produced for all endpoints (Figure 15.1.2.47-49).

The analysis will compare the Day 90 Visit log-transformed values between the CHTP 1.2 and CC arms. An ANCOVA model will be used with terms for sex, average daily CC consumption over the last 6 weeks as reported during admission, log-transformed baseline value and arm. The SAS code will be the same as described in Section 12.5.1.1 “**Primary endpoints**”.

The least squares (LS) means and estimate of the difference along with its 95% CI will be back-transformed before presenting in the tables. The geometric LS means for each arm along with the reduction (i.e: 100% - ratio of CHTP 1.2 : CC (%)) and 95% CI will be presented (Table 15.2.4.30).

All figures, summaries and analyses will be performed on the Per Protocol Populations.

If applicable, the tables with descriptive statistics will be repeated for the group of subjects who attempt to quit (see section “**10.7 Quitters Population**”).

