15.2.4.14	Analysis of NEQ over the exposure period – Per Protocol Population
15.2.4.15	Descriptive Statistics of Plasma Cotinine and Nicotine Concentrations (ng/mL) – Per Protocol Population
15.2.4.16	Analysis of Plasma Cotinine and Nicotine Concentrations over the exposure period – Per Protocol Population
15.2.4.17	Descriptive Statistics of CYP1A2 Activity (%) – Per Protocol Population
15.2.4.18	Analysis of CYP1A2 Activity (%) – Per Protocol Population
15.2.4.19.1	Descriptive Statistics of Spirometry Results – Safety Population
15.2.4.19.2	Descriptive Statistics of Spirometry Results – Per Protocol Population
15.2.4.20.1	Spirometry Interpretation of Clinical Relevance Shift from Baseline- Safety Population
15.2.4.20.2	Spirometry Interpretation of Clinical Relevance Shift from Baseline- Per-Protocol Population
15.2.4.21	Analysis of Spirometry Results – Per Protocol Population
15.2.4.22.1	Summary of Cough Assessments Over Study by Arm – Safety Population
15.2.4.22.2	Summary of Cough Assessments Over Study by Arm – Per Protocol Population
15.2.4.23.1	Summary of Cough Assessments During the Ambulatory Period by Product Use Time Periods – Safety Population
15.2.4.23.2	Summary of Cough Assessments During the Ambulatory Period by Product Use Time Periods – Per Protocol Population
15.2.4.24.1	Summary of Cough Assessments by Arm and Study Day – Safety Population
15.2.4.24.2	Summary of Cough Assessments by Arm and Study Day – Per Protocol Population
15.2.4.25.1	Analysis of Cough during the Confinement Period – Safety Population
15.2.4.25.2	Analysis of Cough during the Confinement Period – Per Protocol Population
15.2.4.26.1	Analysis of Cough during the Ambulatory Period – Safety Population
15.2.4.26.2	Analysis of Cough during the Ambulatory Period – Per Protocol Population
15.2.4.27	Descriptive Statistics of Cardiovascular Risk Endpoints – Per Protocol Population

Tables	Title
15.2.4.28	Analysis of Cardiovascular Risk Endpoints – Per Protocol Population
15.2.4.29	Descriptive Statistics of Risk Endpoints related to Oxidative Stress– Per Protocol Population
15.2.4.30	Analysis of Risk Endpoints related to Oxidative Stress– Per Protocol Population
15.2.5.1	Descriptive Statistics of Questionnaire on Smoking Urges-brief Total and Factor Scores – Per Protocol Population
15.2.5.2	Analysis of Questionnaire on Smoking Urges -brief Factors and Total Scores – Per Protocol Population

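### The Day 90 models for spirometry, cardiovascular, oxidative-stress and CYP1A2 endpoints are per-protocol only, with no companion model in all randomised subjects

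*SAP*

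**What the plan says.** SAP 12.5.2.6 (cardiovascular) and 12.5.2.7 (oxidative stress) both state: "All figures, summaries and analyses will be performed on the Per Protocol Populations". For oxidative stress the only planned model is at Day 90: "The analysis will compare the Day 90 Visit log-transformed values between the CHTP 1.2 and CC arms". SAP 12.5.2.4 handles spirometry the same way: "For the PP population, the analysis will compare the Day 6 and Day 90 Visit values between the CHTP 1.2 and CC arms". For CYP1A2, the list in SAP 13.3.1 has a single model table, 15.2.4.18: "Analysis of CYP1A2 Activity (%) – Per Protocol Population".

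SAP Section 10 provides one safeguard: "If the FAS and PP population differ, the biomarkers of exposure tables will be repeated on the FAS". It does not mention clinical risk endpoints, CYP1A2 or spirometry, and SAP 13.3.1 lists no FAS table for them.

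SAP Table 12 defines ambulatory product non-compliance for the CHTP 1.2 arm only: more than 2 CC in one day, or an average above 0.5 CC per day from Day 1. SAP Section 8 expects minimal PP loss in confinement and in the ambulatory CC arm, but for the other arm only that "at least 50% will remain in the PP set in ambulatory for CHTP 1.2".

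**The concern.** Randomisation makes the arms comparable. A rule that removes subjects from one arm for what they did afterwards undoes that. Smokers who stay almost exclusively on CHTP 1.2 for 90 days may differ from those who do not in motivation, diet, weight change or general health, and each of these can move lipids, inflammatory markers or lung function. A small Day 90 difference could then reflect who stayed in the PP set rather than the product.

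Protocol 4.2 says the ambulatory period should inform on clinical risk and functional endpoints under real-world use. Dual users stay in the study and are measured, so the data exist, but those over the Table 12 limits enter none of these Day 90 models. Protocol 12.3 makes PP the primary set for clinical risk endpoints, not the only one.

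**Working it through.** **1. Analysis sets at Day 90** (table numbers from SAP 13.3.1)

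| Group (secondary objective) | Model table | Set | By-arm summary outside PP |
|---|---|---|---|
| Spirometry (5) | 15.2.4.21 | PP | Safety Population, 15.2.4.19.1 and 15.2.4.20.1 |
| Cardiovascular (6) | 15.2.4.28 | PP | Safety Population for blood pressure, weight, waist, glucose, TG, TC, WBC, platelets |
| Oxidative stress (7) | 15.2.4.30 | PP | None |
| CYP1A2 (8) | 15.2.4.18 | PP | None |

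Fourteen laboratory endpoints are outside the safety panel (SAP Table 18) and so have no by-arm summary beyond PP: hs-CRP, MPO, LDL, HDL, fibrinogen, homocysteine, HbA1c, Apo A1, Apo B, sICAM-1, 11-DTX-B2, 8-epi-PGF2α, 8-OHdG and TAC.

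**2. The plan's own figure.** SAP Table 11 gives 98% power for total NNAL at Day 90. Inputs: mean ratio 0.30, CV 0.60, threshold 0.50, one-sided 2.5%.
- Log-scale difference: ln(0.50/0.30) = 0.511. SD: √ln(1 + 0.60²) = 0.555.
- 40 v 40: SE = 0.555 × √(1/40 + 1/40) = 0.124; power = Φ(0.511/0.124 − 1.96) = 98.5% (98.3% with the t distribution).
- 80 v 40: power = 99.7%.

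The stated 98% fits 40 retained of 80 better, so the plan itself budgets for one-sided loss at Day 90.

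**3. Size of a possible bias.** Assumptions, none from the documents: no true effect; all 40 CC subjects kept; a fraction p of the CHTP 1.2 arm kept; compliers differ from non-compliers by d SD in the favourable direction.
- Shift of the PP contrast = d(1 − p). With p = 0.5 the shift is 0.5d.
- SE = √(2/40) = 0.2236 SD. One-sided error = Φ(−1.96 + shift/SE).
- With baseline adjustment: correlation 0.7, so SE = 0.2236 × √(1 − 0.49) = 0.160. Adjustment is also assumed to remove 70% of the shift. This is a separate assumption; it coincides with the correlation if compliers differ as much at baseline as at Day 90.

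| d (SD) | Shift | Error, unadjusted | Residual shift | Error, adjusted |
|---|---|---|---|---|
| 0.2 | 0.10 | 6.5% | 0.030 | 3.8% |
| 0.3 | 0.15 | 9.9% | 0.045 | 4.7% |
| 0.5 | 0.25 | 20% | 0.075 | 6.8% |

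With 70% retained (56 subjects) and d = 0.3, the shift is 0.3 × 0.3 = 0.09 and the SE is √(1/40 + 1/56) = 0.207. Error is 6.4% unadjusted and 3.8% adjusted.

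A second unadjusted illustration selects on a latent adherence trait correlated 0.1 to 0.4 with the outcome. It gives 5.4% to 29.7% at 50% retention, 4.3% to 15.9% at 70% and 3.1% to 5.9% at 90%.

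The adjusted column suits the fourteen laboratory endpoints, whose models include baseline. For spirometry and CYP1A2, the terms listed in SAP 12.5.2.4 and 12.5.2.3 omit baseline while the cross-referenced code includes it, so either column could apply.

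**4. Precision.** For FAS 80 v 40, SE = √(1/80 + 1/40) = 0.194 SD, against 0.224 for PP 40 v 40. The 95% CI half-widths are 0.38 and 0.44 SD (complete data, no covariate gain).

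**The case against.** A reader might infer that secondary objectives 5 to 8 have no randomised comparison at all. The documents do not support that.
- Objective 5 includes cough, which is also modelled outside PP: "Analysis of Cough during the Confinement Period – Safety Population" is a listed table, and SAP 12.5.2.5 says of it: "For the confinement period, a similar model will be run, replacing the product use category with the treatment arm".
- Spirometry and several objective 6 measures have Safety Population tables. Every enrolled subject is due to test CHTP 1.2 before randomisation, and SAP 10.6 departs from the randomised arm only if the site consistently gave the wrong product. These summaries are therefore essentially as randomised.
- Models at Day 5 or 6 exist for spirometry, CYP1A2 and, where applicable, cardiovascular endpoints; few exclusions are expected there.
- Sections 12.5.2.6 and 12.5.2.7 also allow descriptive tables in quitters drawn from the FAS, and individual data are listed.

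All of this stands. None of it supplies a Day 90 model in all randomised subjects for the four groups.

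It can also be said that PP was prespecified, that the objectives concern smokers who switch, and that these are secondary endpoints reported as estimates with confidence intervals. That supports keeping PP primary but does not argue against a sensitivity analysis. Finally, the FAS tables listed for exposure biomarkers are themselves descriptive; their model tables (15.2.3.1, 15.2.4.1) are PP only. This is correct. It means that widening the Section 10 sentence would not be enough unless the model tables are named.

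**Conclusion.** The concern holds in a limited form: spirometry, cardiovascular, oxidative-stress and CYP1A2 endpoints have no modelled Day 90 comparison of all randomised subjects, and the planned PP contrast rests on one-sided selection after randomisation. For objective 7 this needs no qualification, because its only model is at Day 90 in PP.

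The size is uncertain. At 50% retention and d of 0.2 to 0.5 SD, one-sided error is about 3.8% to 6.8% with baseline adjustment and 6.5% to 20% without. Both ranges rest on assumed inputs and on the lowest retention the plan allows. Quoting roughly 10% as the expected error would overstate the case for the fourteen laboratory endpoints, whose models adjust for baseline. If compliers differ in the unfavourable direction, the bias runs the other way.

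It might also be inferred that every statement about switching must rest on the FAS. That does not follow. SAP 6.3.3.1 anticipates dual use, so the FAS estimates the effect of being assigned to CHTP 1.2. The two sets answer different questions, and reporting both lets the reader see how far selection matters.

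**What to change.** Keep PP as the primary set. Add FAS versions by randomised arm, beside the PP results and labelled as a sensitivity analysis, of:
- model tables 15.2.4.18, 15.2.4.21, 15.2.4.28 and 15.2.4.30;
- descriptive tables 15.2.4.17, 15.2.4.27 and 15.2.4.29.

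Extend the repeat sentence in SAP Section 10 to cover biomarkers of exposure, clinical risk endpoints, CYP1A2 and spirometry. Amend the PP-only sentences in 12.5.2.4, 12.5.2.6 and 12.5.2.7 to match, and name the new tables in 13.3.1.

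No new data are needed; the same programs run on another population flag. The costs are a few extra tables and a FAS estimate that dual use may dilute, which the report should state.

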12.5.2.7 Risk Endpoints related to Oxidative Stress

The following risk endpoints related to oxidative stress will be assessed:

- Epi-prostaglandin F2 α (8-epi-PGF2 α) in 24-hour urine at baseline, Day 5, Day 30 Visit, Day 60 Visit, and Day 90 Visit (expressed as concentration adjusted for creatinine)
- Ratio of 8-epi-prostaglandin F2 α (8-epi-PGF2 α) to prostaglandin F2 α (PGF2 α) in plasma at baseline, Day 5 and Day 90 Visit (results only listed).
- 8-Hydroxy-2'-deoxyguanosine (8-OHdG) in 24-hour urine at baseline, Day 5, Day 30 Visit, Day 60 Visit, and Day 90 Visit (expressed as concentration adjusted for creatinine)
- Total anti-oxidant capacity (TAC) in serum at baseline, Day 5 and Day 90 Visit.

It is assumed that all oxidative stress parameters are log-normally distributed.

These clinical risk endpoints will be summarized and listed by arm, subject, parameter and time point, together with changes from baseline (Listing 15.3.4.6).

The actual values, along with the percent change from baseline will be summarized (Table 15.2.4.29).

The profiles of geometric means per time point will be produced for all endpoints (Figure 15.1.2.47-49).

The analysis will compare the Day 90 Visit log-transformed values between the CHTP 1.2 and CC arms. An ANCOVA model will be used with terms for sex, average daily CC consumption over the last 6 weeks as reported during admission, log-transformed baseline value and arm. The SAS code will be the same as described in Section 12.5.1.1 “**Primary endpoints**”.

The least squares (LS) means and estimate of the difference along with its 95% CI will be back-transformed before presenting in the tables. The geometric LS means for each arm along with the reduction (i.e: 100% - ratio of CHTP 1.2 : CC (%)) and 95% CI will be presented (Table 15.2.4.30).

All figures, summaries and analyses will be performed on the Per Protocol Populations.

If applicable, the tables with descriptive statistics will be repeated for the group of subjects who attempt to quit (see section “**10.7 Quitters Population**”).

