7. To evaluate the changes in levels of selected clinical risk endpoints related to oxidative stress over the entire exposure period in smokers switching from CC to CHTP 1.2 as compared to smokers continuing to use CC
- Endpoints (Day 5 to Day 90 Visit):
- Epi-prostaglandin F2 α (8-epi-PGF2 α) in 24-hour urine on Day 5, at Day 30 Visit, Day 60 Visit, and Day 90 Visit (expressed as concentration adjusted for creatinine).
 - Ratio of 8-epi-prostaglandin F2 α (8-epi-PGF2 α) to prostaglandin F2 α (PGF2 α) in plasma on Day 5 and at Day 90 Visit.
 - 8-Hydroxy-2'-deoxyguanosine (8-OHdG) in 24-hour urine on Day 5, at Day 30 Visit, Day 60 Visit, and Day 90 Visit (expressed as concentration adjusted for creatinine).
 - 4-Hydroxy-2-nonenal (4-HNE) in serum on Day 5 and at Day 90 Visit^a.
 - Total anti-oxidant capacity (TAC) in serum on Day 5 and at Day 90 Visit.
- ^a Samples for 4-HNE analysis have been collected but will not be analyzed due to the failure to develop a selective and quantitative assay
8. To describe the change in cytochrome P450 1A2 (CYP1A2) enzymatic activity in smokers switching from CC to the CHTP 1.2 as compared to smokers continuing to use CC
- Endpoint (Day 5 and Day 90 Visit):
- Molar metabolic ratio of paraxanthine/caffeine in plasma
9. To monitor the safety profiles associated with CHTP 1.2 and CC during the study
- Endpoints:
- Adverse events (AEs) / serious adverse events (SAEs) and incidence of CHTP 1.2 malfunctions and misuse, including the incidence of heat source drop off
 - Vital signs
 - Electrocardiogram (ECG)
 - Clinical chemistry, hematology, and urine analysis safety panel
 - Physical examination
 - Concomitant medications

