6.3.3 Compliance to Product Allocation

During the confinement period, adherence to product allocation for both study arms will be ensured by strict distribution of the products (stick by stick) and collection of the CC butts and CHTP 1.2 after each use. Distribution and return of these products will be documented in appropriate logs.

During the ambulatory period, from Discharge on Day 6 until Discharge at Day 90 Visit, subjects in both study arms will capture the number of the product used (e.g., menthol and non-menthol CC, CHTP 1.2, or any other tobacco /nicotine-containing products including nicotine replacement therapy [NRT]) in the product use diary on a daily basis. The product use diary will be supplied by Sponsor and distributed to the subjects by the study site collaborators. The data captured in the product use diary will serve as the method to assess adherence in both arms. On Day 6, the adherence to the assigned product will be ensured using both the accountability log (from 06:30 AM until Discharge) and the product use diary (in the subjects daily report of product use). In case of discrepancy between the log and the diary entries, the diary will be considered as the primary source data.

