6.3.3.1 Dual Use

[figure not shown]
Although subjects are being requested to use solely the product allocated to them in their respective study arm, it is considered that during the ambulatory period not all subjects randomized to CHTP 1.2 arm might be exclusively using CHTP 1.2 at all times during the study. Subjects may concomitantly use CHTP 1.2 and CC (dual-use).

To assess dual-use of CHTP 1.2 and CC, PMI has defined product use categories defined by the percentage of the reported CHTP 1.2 Tobacco Sticks consumption during each time period of interest. The percentage use of CHTP 1.2 will be calculated by:

$$100 \times \frac{\text{Total number of CHTP 1.2 products used}}{\text{Total number of CHTP 1.2 products used} + \text{Total number of CC smoked}}$$

Product use categories are summarized in **Table 7**, and **Figure 2** presents a detailed overview of the definition of the product use categories.

Figure 2 Product Use Pattern Categorization

The more granular categorization scheme will be used for the description of the product use patterns observed in the study whereas the less granular scheme will be used for the presentation of other study endpoints (e.g. safety endpoints) to better understand the impact of product.

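### Oxidative-stress markers have Day 5 as a named endpoint timepoint, but the SAP plans an adjusted between-arm comparison at Day 90 only

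*SAP*

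**What the plan says.** Objective 7 (Protocol 3.2, SAP 5.2) is to evaluate changes in oxidative-stress markers across the whole exposure period, CHTP 1.2 against CC, with endpoints from Day 5 to Day 90.

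- **Urinary 8-epi-PGF2α and 8-OHdG** are each defined "in 24-hour urine on Day 5, at Day 30 Visit, Day 60 Visit, and Day 90 Visit (expressed as concentration adjusted for creatinine".
- **TAC** is defined as "Total anti-oxidant capacity (TAC) in serum on Day 5 and at Day 90 Visit".
- **The plasma 8-epi-PGF2α to PGF2α ratio** is kept but not tested: "in plasma at baseline, Day 5 and Day 90 Visit (results only listed".
- **4-HNE** samples exist but "will not be analyzed due to the failure to develop a selective and quantitative assay".

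Three markers therefore remain for inference. For these, SAP 12.5.2.7 states: "The analysis will compare the Day 90 Visit log-transformed values between the CHTP 1.2 and CC arms". The model is the primary-endpoint ANCOVA (log baseline, sex, cigarette consumption, arm), reported in Table 15.2.4.30. All timepoints are summarized by arm in Table 15.2.4.29 and plotted in Figures 15.1.2.47 to 15.1.2.49. Everything in the section uses the per-protocol populations.

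The preceding section, 12.5.2.6 on cardiovascular endpoints, says: "For all endpoints, an ANCOVA model will be used on Day 5 and on the Day 90 Visit (as applicable". SAP 12.5.2.3 compares CYP1A2 activity on both Day 5 and Day 90.

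**The concern.** Day 5 and Day 90 are different kinds of comparison. In confinement, "adherence to product allocation for both study arms will be ensured by strict distribution of the products (stick by stick". In the ambulatory period the SAP expects that "not all subjects randomized to CHTP 1.2 arm might be exclusively using CHTP 1.2 at all times during the study", and use is self-reported in a diary. SAP Table 12 then defines ambulatory non-compliance by cigarette use in the CHTP 1.2 arm only (more than 2 CC on one day, or an average above 0.5 CC per day). Day 90 thus compares switchers selected on adherence after randomization with smokers not selected in that way. SAP section 10 repeats only the biomarker-of-exposure tables on the FAS, so these markers have no unselected counterpart.

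Day 5 is the timepoint closest to the randomized comparison, and it has no baseline-adjusted estimate or CI for the arm ratio. A reader wanting one would have to build it from two separate arm summaries, without the baseline, sex and consumption adjustment used at Day 90. SAP section 9 gives no reason for the difference.

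**Working it through.** **1. What is modelled on Day 5 elsewhere.**

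| Marker | Scheduled on Day 5 | Between-arm model on Day 5 | Between-arm model at Day 90 |
|---|---|---|---|
| 11-DTX-B2 (24-h urine) | yes | yes (12.5.2.6) | yes |
| 8-epi-PGF2α (same urine collection) | yes | no | yes |
| 8-OHdG (same urine collection) | yes | no | yes |
| TAC (serum) | yes | no | yes |
| CYP1A2 | yes | yes (12.5.2.3) | yes |

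The three urinary markers share one row of the 24-hour urine schedule (Protocol Table A2, SAP Table A1). The Day 5 sentence in 12.5.2.6 does not fill the gap, because that section's list contains none of the three oxidative-stress markers.

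**2. Checking the sample sizes against the plan's power.** No power is stated for the oxidative-stress markers, so the primary endpoints in SAP section 8 serve as the check. With sd = √ln(1 + CV²), δ = ln(0.5/MR) and one-sided alpha 0.025, power = Φ(δ/SE − 1.96).

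- COHb on Day 5: MR 0.40, CV 0.32, so sd = 0.312 and δ = 0.223. At 80 v 40, power is 95.8% (stated 96%). At 40 v 40 it would be 89.2%, which does not reproduce the stated figure.
- Total NNAL at Day 90: MR 0.30, CV 0.60, so sd = 0.555 and δ = 0.511. At 40 v 40, power is 98.5% (stated 98%). At 80 v 40 it is 99.7%, so 40 v 40 fits better but is not the only possibility.

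This supports 80 v 40 on Day 5 and is compatible with 40 v 40 at Day 90.

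**3. Precision, for equal SD.** SE is proportional to √(1/n₁ + 1/n₂).

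- Day 5, 80 v 40: √(1/80 + 1/40) = 0.194
- Day 90, 40 v 40 (50% retention in the CHTP 1.2 arm): √(1/40 + 1/40) = 0.224; ratio to Day 5 = 1.155
- Day 90, 60 v 40: √(1/60 + 1/40) = 0.204; ratio = 1.054
- Day 90, 80 v 40: ratio = 1.00

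**4. What each timepoint could detect.** The documents give no CV for these markers. Assuming 0.3, 0.5 or 0.7, and ignoring any gain from covariates, the reduction detectable with 80% power is 1 − exp(−(1.960 + 0.842) × sd × √(1/n₁ + 1/n₂)).

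| Assumed CV | Day 5, 80 v 40 | Day 90, 40 v 40 |
|---|---|---|
| 0.3 | 14.7% | 16.8% |
| 0.5 | 22.6% | 25.6% |
| 0.7 | 29.0% | 32.7% |

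**The case against.** The sponsor has a reasonable defence, and much of it stands.

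- **No test was promised.** Protocol 12.5.3 commits secondary endpoints only to descriptive summaries, and the confirmatory hypothesis in 12.4.4 concerns biomarkers of exposure. A reader might infer a departure from the protocol; there is none.
- **Day 5 is reported.** Each arm's values appear with 95% CIs. A reader might infer that the objective is answered only where selection can bias it. That goes too far: only the adjusted contrast is absent.
- **Day 90 has a partial rationale.** Protocol 4.2 links the ambulatory period with changes in clinical risk endpoints and cites a fall in 8-epi-PGF2α after 1 to 3 months of cessation. It gives no time course for 8-OHdG or TAC. Where the effect grows with time, Day 90 may be the more sensitive timepoint: even at 40 v 40, Day 5 loses its precision advantage if its log-scale effect is below about 87% of the Day 90 effect (1/1.155).
- **The parallel with other sections is narrow.** Read literally, the cardiovascular Day 5 model covers only 11-DTX-B2, because the other markers in that list are taken on Day 6 or only at later visits. BoExp and exhaled CO measure exposure, for which Day 5 is a natural test point. CYP1A2 and 11-DTX-B2 are the clean parallels.
- **Adding Day 5 does not cover the whole period.** Days 30 and 60 would still be unmodelled for the two urinary markers.

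None of this explains why two markers from the same Day 5 urine collection as 11-DTX-B2 are treated differently from it.

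**Conclusion.** The point holds as a low-priority improvement. The plan leaves without an adjusted between-arm estimate the one timepoint for these three markers at which use was enforced and exclusions are expected to be minimal. The only modelled timepoint is per-protocol, with the cigarette-use limits applied to one arm.

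The precision cost ranges from none to about 15% in SE. A reader might take 15% as the expected loss, but the plan says at least 50% will be retained, so it is the upper end. The range assumes equal SDs at both timepoints, 80 v 40 on Day 5, and no loss in the CC arm. The effect of selection at Day 90 cannot be sized from the documents. Nor do they support calling Day 90 the weaker timepoint overall, since they give no effect sizes for these markers.

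**What to change.** In SAP 12.5.2.7, change the analysis sentence so that it names Day 5 as well as the Day 90 Visit. Use the same ANCOVA, with the Period 1 per-protocol population for Day 5 and the Period 4 population for Day 90. Report the geometric LS mean ratios with 95% CIs for both days in Table 15.2.4.30.

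Two details should be settled in the same edit:

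- **Direction for TAC.** SAP 12.1.8 defaults to one-sided tests and the tables report reductions, but Protocol 4.2 treats a decrease in TAC as adverse. The test direction for TAC should be stated.
- **Display of p-values.** SAP 12.5.2.1.2 shows the Day 90 p-value for urinary BoExp only if Day 5 was significant. The text should say whether that rule applies here.

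If the sponsor prefers to keep Day 5 descriptive, one sentence giving the reason would close the point.

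The cost is small: the data are already scheduled and the code exists. The comparisons for these markers rise from three to six, unadjusted like all secondary endpoints under 12.1.8. The change should be made before database lock, as SAP section 3 requires for amendments; after that, 13.3 would have it reported as an unplanned analysis.
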